3.2 Subject disposition

According to the protocol, a subject who failed screening can be rescreened under a new subject ID. If a patient was randomized after rescreening, a rescreening log was completed to document the original subject ID the patient was assigned. However, if a patient failed a rescreening, no rescreening log was completed. As a result, there is not enough information from the clinical database to identify the number of unique patients who were screened/rescreened for this study. Only the number of unique subject IDs that had been assigned for each screening/rescreening are available. Therefore, the total number of screenings will be presented, along with the reason for each failed screening.

For patients who failed a screening and were later randomized, the reason for first failed screening will also be summarized.

A listing with all the screening/rescreening under a unique subject ID will be provided.

Subject disposition for study and study treatment will be summarized on the RAN set. The number and proportion of subjects who complete the study or discontinue the study prematurely along with the reason for discontinuation will be summarized by randomized treatment assignment. The number and proportion of subjects who discontinue the study drug prematurely along with the reason for study drug discontinuation will be summarized by randomized treatment assignment.

Subjects who discontinue early from the study treatment or those who complete the study treatment according to the study design but decide not to enter the extension study, will have a 3-month follow up visit. The number and proportion of the subjects who missed follow up visit, along with the reason, will also be summarized on the RAN set.

The number and proportion of subjects in each analysis set will be presented by treatment group.

3.3 Protocol deviation

Protocol deviations will be summarized by deviation categories and treatment for the RAN set. In addition, protocol deviations that led to exclusion from PPS will be summarized by deviation category, deviation terms and treatment groups for the RAN set.

Additionally, unblinding per protocol due to safety reasons may occur during the study. If a subject's treatment code is revealed to any observer or study center personnel who are intended to be blinded during the evaluation period (as marked on the study completion eCRF page), that subject will also be excluded from the PPS. A summary of those subjects will also be presented for the RAN set.

3.4 Demographics and other baseline characteristics

Subject demographics and other baseline characteristics include age, gender, race, and ethnicity collected on the demography eCRF, height and body weight recorded at baseline on the vital signs eCRF, body mass index (BMI) calculated as (body weight in kilograms) / (height in meters)² at baseline, pubertal status based on Tanner stage assessed at screening

visit (pre-pubertal if Tanner staging score <2; pubertal if Tanner staging score \geq 2 or missing given an observation of bone age \geq 16 yrs), and pubertal status (from interactive IVRS, i.e., I based on investigator assessment) at the randomization visit. Age will be calculated from date of first dose of study drug and date of birth. For subjects without a first dose date, date of randomization visit will be used.

The race will be reported using the designations (different from the categories used on the CRF) shown on Table 3-2.

Table 3-2 Designations for race in analysis

Race collected on CRF	Designations for Race in analysis	Race (shortened version in ASR)
Native American	American Indian or Alaska Native	Age/Sex/AI
Asian	Asian	Age/Sex/AS
Black	Black or African American	Age/Sex/BL
Pacific islander	Native Hawaiian or other Pacific Islander	Age/Sex/NH
Caucasian	White	Age/Sex/WH
Other	Other	Age/Sex/OT

ASR: age, sex, race variable.

These variables will be summarized on the RAN set by presenting frequency distributions (for categorical variables) or descriptive statistics of mean, standard deviation, minimum, median and maximum (for continuous variables).

For baseline comparability analysis, categorical variables will be analyzed by Cochran-Mantel-Haenszel (CMH) test stratified by region and pubertal status; continuous variables will be analyzed using ANOVA with covariates of treatment, region, and pubertal status. This analysis will be performed on the RAN set and will be presented in Appendix 16.1.9 only. For categorical variables, the number and percentage of subjects with missing data will be provided but those subjects who are in the missing category will not be included in the denominator for the CMH test.

Note that these tests of comparability are performed for descriptive purposes only, and will not serve as a basis for determining entry of explanatory variables into the respective models. However, when these tests yield significant results they can be used as supportive information in interpreting the statistical analyses performed on the primary and secondary efficacy variables.

3.5 MS disease and medical history

3.5.1 MS baseline disease characteristics

MS baseline disease characteristics, MS disease history, MS medication history, and MS related eye history will be summarized by treatment group for the RAN set.

MS baseline characteristics include baseline EDSS, key MRI parameters (e.g., number and volume of Gd-enhancing lesions, number and volume of T2 lesions, volume of T1 hypointense lesions, and normalized brain volume)

MS disease history includes duration of MS since diagnosis (years), duration of MS since first symptom (years), number of relapses as well as the number of relapses that required steroid treatment (in the last 12 months prior to randomization visit, between the last 12 to 24 months prior to randomization visit, and in the last 24 months prior to randomization visit), and time since onset of most recent relapse (months). Duration of MS since diagnosis (years) will be derived as $[(\text{first dose date} - \text{MS diagnosis date} + 1)/365.25]$; duration of MS since first symptom (years) will be derived as $[(\text{first dose date} - \text{first MS symptom date} + 1)/365.25]$; and time since onset of most recent relapse (months) will be derived as $[(\text{first dose date} - \text{most recent relapse onset date} + 1)/30]$. For subjects without a first dose date, date of randomization visit will be used.

For the MS diagnosis date and the first MS symptom date, a partial date will be imputed as follows: a) if only year yyyy is available, the imputed date will be 1-July-yyyy; b) if both year yyyy and month mmm are available, the imputed date will be 15-mmm-yyyy.

For the most recent relapse onset date, a partial date will be imputed as follows: a) if only year yyyy is available, the imputed date will be 1-Jan-yyyy; b) if both year yyyy and month mmm are available, the imputed date will be 01-mmm-yyyy.

MS medication history of previous disease-modifying drugs (coded by WHO drug dictionary) will be summarized by preferred term (PT). The number and proportion of treatment-naïve subjects (i.e., subjects who have not been treated with any disease-modifying drug before study enrolment) will also be presented.

MS related eye history includes history data collected at screening visit on the ophthalmologic examination eCRF.

3.5.2 Medical history

Any condition entered on the relevant medical history/current medical conditions eCRF will be coded using MedDRA. The relevant medical history and continuing medical conditions will be summarized by primary system organ class (SOC), preferred term (PT) and treatment group for the RAN set.

3.6 Treatments (study medication, rescue medication, other concomitant therapies)

3.6.1 Study medication

The duration (days) of intake to randomized study medication will be summarized on the SAF set by presenting the number (and percentage) of subjects taking the study medication for a minimum duration of time as specified in Table 3-3. Duration in terms of number of days as shown in the second column will be used in the summary tables. Summary statistics of duration to study medication will also be presented. The exposure to the actual study medication taken will also be presented in the pre-pubertal (Tanner staging score <2) and young subjects (<=12 years) subgroups.

Duration of study medication intake is the number of days on study drug during the study. The days when the subject does not take the study drug will be excluded. That is, duration

will exclude periods of temporary interruption of study medication. Only data from the core phase will be included. See [Section 3.8.3](#) for definition of core phase data.

For each treatment group, the patient-years calculated as (the sum of the number of days on study drug for all subjects in the group)/365.25, will also be presented.

3.6.2 Drug accountability

To measure compliance, the number of study drug capsules/ syringes dispensed and returned from the drug accountability page at each visit will be used to derive the drug accountability rate for each patient:

$$\text{Drug accountability rate (\%)} = \frac{\# \text{ capsules/syringes dispensed} - \# \text{ capsules/syringes returned}}{\# \text{ capsules/syringes expected to be taken}} * 100,$$

where:

capsules/syringes expected to be taken is assuming the consumption of one capsule per day or one injection per week during the treatment period recorded on drug accountability form:

capsules expected to be taken = date of last dose from drug dispensed - date of first dose from drug dispensed + 1

syringes expected to be used = ceil ((date of last dose from drug dispensed - date of first dose from drug dispensed + 1) / 7)

The Drug accountability rate will be summarized by treatment for fingolimod/placebo and IFN β-1a/placebo.

Table 3-3 Time-intervals used to summarize study medication intake

Duration	Duration in terms of number of days
Any	≥1 day
≥1 week	≥7 days
≥2 weeks	≥14 days
≥1 month	≥30 days
≥2 months	≥60 days
≥3 months	≥90 days
≥6 months	≥180 days
≥9 months	≥270 days
≥12 months	≥360 days
≥15 months	≥450 days
≥18 months	≥540 days
≥21 months	≥630 days
≥24 months	≥720 days
≥25 months	≥750 days

3.6.2.1 Overall Patient-year by subgroup

The overall Patient –year within each treatment arm by 1) age category (<=12 yrs vs. >12 yrs) and gender as well as 2) by race will be provided to support RMP report.

3.6.3 Concomitant and rescue therapy

Records on the Concomitant medications / significant non-drug therapies eCRF will be coded using WHO drug dictionary. All medications will be classified as *prior* and *concomitant* medication and summarized by treatment group and preferred term as follows:

- *Prior* medications are defined as drugs taken and stopped prior to first dose date of study medication and will be summarized for SAF.
- *Concomitant* medications are defined as drugs taken at least once on or between first dose date and last dose date of study medication (including those which were started prior to first dose and continued into the treatment period) and will be summarized for SAF.
- *Post-study drug discontinuation* medications will be drugs started after the discontinuation of randomized study medication and will be summarized for FUS.

Medications will be categorized into one (and only one) of above classes based on recorded or imputed start and end dates.

Incomplete or missing end date should be imputed as follows:

- If only day is missing (XXMONYEAR), it should be imputed with last day (LD) of the month (LDMONYEAR),
- If day and month are missing (XXXXXXYEAR), it should be imputed with last day of December (LDDECYEAR,)
- If the whole date is missing (XXXXXXXXXX), it should be imputed with last day of December of the cut-off year (LDDECCUTOFFYEAR). The cut-off year will be defined as the year of database lock.

Incomplete or missing start date should be imputed as follows.

- If the year value is missing, it will be imputed as the date one day after the treatment start date.
- If the year value is less than the treatment start date year value, it will be imputed as the midmonth date (15MONYYYY) or the midyear date (01JulYYYY) if the month is missing.
- If the year value is greater than the treatment start date year value, it will be imputed as the month start date (01MONYYYY) or the year start date (01JanYYYY) if the month is missing.
- If the year value is equal to the treatment start date year value, it will be imputed as the midmonth date (15MONYYYY) if the month is less than the treatment start month or as the start month date (01MONYYYY) if the month is greater than the treatment start month. In case the month is either missing or equal to the treatment start month, it will be imputed as the date one day after the treatment start date.

3.6.3.1 Steroid for treatment of MS relapses during the study

Corticosteroids used for the treatment of multiple sclerosis relapses that started after the initiation of study medication will be listed.

3.7 Pooling of centers

This study will be conducted in centers worldwide. In order to minimize the impact of low-enrolling countries on the analysis (such as non-convergence of the analysis model), countries are pooled into regions based on geographical proximity and regions will be used in the analysis as a stratification factor.

3.8 Visit windows and cutoffs for efficacy and safety analyses

This section defines the data cutoffs within which data will be included in the analysis and time points for which data will be summarized.

Due to the study design, data collected at the time of study drug discontinuation or treatment completion will be recorded in the eCRF at end of treatment visit (corresponding to Visit 777 in the database). In the subject completion (CMP) data set, data collected from the study drug discontinuation eCRF (Visit 777) and study phase completion eCRF (Visit 778) will be differentiated by the visit number although there is no study visit corresponding to Visit 778.

3.8.1 Study Day 1 and other study days

Study Day 1 (or Day 1) is defined as the first day of administration of randomized study medication (i.e., the first dose date of the study drug).

All other study days will be labeled relative to Day 1. For event dates on or after Day 1, study day for an event date is calculated as (event date – first dose date + 1), which could be Day 1, Day 2, Day 3, etc. For event dates before Day 1, study day for an event date is calculated as (event date – first dose date), which could be Day -1, Day -2, etc., referring to one day, two days, etc., before Day 1, respectively. Duration of an event will be calculated as (event end date – event start date + 1). One month is defined as 30 days. Day 0 will not be used.

3.8.2 Baseline

In general, a baseline value refers to the last measurement made prior to the administration of the first dose of the study drug. Assessments made on Day 1 may occur before or after the first dose. The following rules will be applied to determine which record is the last measurement prior to the first dose (i.e., the baseline value).

- Consider all records with an assessment date before the first dose date or with an assessment date on the same day of the first dose date and from Day 1 visit or before (i.e., visit\repeat visit number < 3). Baseline is the last record after sorting all above records with respect to assessment date, visit and repeat visit number.
- Some data specific rules for determining baseline will be applied as described below or in data specific sections if applicable.

For vital signs, the mean of the Day 1 pre-dose value will be used as baseline. If unavailable, the last available (including unscheduled) value before the first dose will be used.

For ECG, the Day 1 pre-dose value will be used as baseline. If unavailable, the last available (including unscheduled) value before the first dose will be used.

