A neuroradiologist will be responsible for:

- Previewing each MRI scan performed for the study patients
- Contacting the Primary Treating Physician in case of unexpected findings detected on the MRI scan

Ophthalmologist

- The Ophthalmologist will perform the ophthalmic examinations as per protocol

Pulmonary Function Test Laboratory Technician

- Pulmonary function test (PFT) technician will perform PFTs per local standard practice for pediatric patients

6 Visit schedule and assessments

The Core Phase will consist of two periods: a pre-randomization period consisting of screening and baseline visits, and a double-blind treatment period. The Extension Phase consists of a fingolimod treatment period.

The day of randomization in the Core Phase is defined as Day 1 of the study (Visit 3), which is the first day of study drug administration. Entry in the Extension Phase occurs at Visit 15 immediately following the completion of the Core Phase.

[Table 6-1](#), [Table 6-2](#) and [Table 6-3](#) lists all assessments and indicates with an “X” the visits when they are performed.

Patients should follow the visit schedule with an allowed visit window as follows:

- ± 2 days for Visit 4 and Visit 16
- ± 5 days for Visit 5 and all monthly visits
- ± 10 days for all quarterly and biannual visits
- + 14 days for Visit 15 (should be completed within 14 days of completion of Visit 14 / EOS-CP). Date of completion of Core Phase should be entered in the Study phase completion eCRF (date entered should be 1 day before Visit 15; first Extension Phase visit). Study drug should not be interrupted between the end of the Core Phase and the start of the Extension Phase.

Visit windows can be extended on a case-by-case basis to accommodate scheduling (please consult Sponsor for approval). The pre-randomization period may be extended with approval from the sponsor on a case by case basis to accommodate additional time needed to complete the screening assessments (e.g., additional lab tests, time to be (re)vaccinated, time to allow lab parameters to come within protocol requirements, etc.).

In addition to the scheduled visits, patients may have unscheduled visits following an onset of an MS relapse or for safety follow-up.

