3.8.4.2 Visits windows

For data not listed in [Section 3.8.4.1](#), visit-windows will be defined and used for the by-visit summaries. Visit-windows will only be defined for post-baseline visits and applied to post-baseline data (including both scheduled and unscheduled visit). Based on the study assessment schedule as specified in the study protocol, visit-windows are defined by a set of days around each nominal visit target day.

Visit-windows for vital signs, laboratory assessments, ophthalmologic examination (excluding OCT), pulmonary function tests, and ECG are provided in Table 3-4 to Table 3-9. These visit-windows will not be applied to any data related to the first dose or second dose or restart dose monitoring which will be summarized separately.

When visit-windows are used, all post-baseline visits will be re-aligned, i.e., they will be mapped into one of the visit-windows. E.g., if a subject's *Month 1* visit is delayed and occurs on Day 47, then it will be re-aligned to visit-window *Month 2*. As a result, it is possible that several assessments may fall into one particular visit-window. Statistical approaches to handle multiple visits in a given visit-window are described in [Section 3.8.6](#). Tables displaying summary statistics "by visit" will also use the term visit-window as column header; this is to remind the reviewer that multiple assessments of a subject might be summarized.

Table 3-4 Visit-windows for vital signs, physical development, and laboratory values (hematology/blood chemistry other than liver panel)

Visit	Start day	Target Day	End day
Week 2	1	14	22
Month 1	23	30	45
Month 2	46	60	75
Month 3	76	90	135
Month 6	136	180	225
Month 9	226	270	315
Month 12	316	360	405
Month 15	406	450	495
Month 18	496	540	585
Month 21	586	630	675
Month 24	676	720	765

Table 3-5 Visit-windows for urinalysis

Visit	Start day	Target Day	End day
Month 6	1	180	270
Month 12	271	360	540
Month 24	541	720	765

Table 3-6 Visit-windows for liver panel

Visit	Start day	Target Day	End day
Week 2	1	14	22
Month 1	23	30	37
Month 1.5	38	45	52
Month 2	53	60	75
Month 3	76	90	105
Month 4	106	120	135
Month 5	136	150	165
Month 6	166	180	225
Month 9	226	270	315
Month 12	316	360	405
Month 15	406	450	495
Month 18	496	540	585
Month 21	586	630	675
Month 24	676	720	765

Table 3-7 Visit-windows for ophthalmologic examination (excluding OCT)

Visit	Start day	Target Day	End day
Month 3	1	90	135
Month 6	136	180	225
Month 9*	226	270	315
Month 12*	316	360	450

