3.8.6 Multiple assessments within visit windows

For visit windows defined in [Sections 3.8.4.2](#) and [3.8.5](#), multiple records may exist in one particular visit window. All results (scheduled and unscheduled) will be displayed in listings, but only one value (observed or derived) “representing” the subject will be selected for summary statistics by visit-window. The following rules (unless otherwise specified) will be applied to obtain one value per subject per visit-window which will be used in the by-visit summaries.

- For quantitative variables (i.e., continuous variables for which summary statistics and change from baseline tables will be provided), the average of the multiple records will be used.
- For qualitative variables (i.e., binary or nominal variables for which incidence rates and frequency distribution tables will be provided), the worst record (from scheduled and unscheduled visits) will be used. It is noted that in the analyses performed, worst case is always well defined.

Note that “Last assessment on study drug” is not like other visit-windows where multiple assessments could occur. The assessment to be summarized at that time point is the last on drug observation which is the last observation a subject has while he or she is on study drug. Therefore, the above multiple assessment rules do not apply.

In addition, the multiple assessment rules do not apply to the first dose/second dose/dose increase/restart dose monitoring data.

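### SAP 3.8.2 contradicts itself on whether a pre-dose record from the Day 1 visit (Visit 3) can be the baseline value

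*SAP*

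**What the plan says.** SAP 3.8.2 opens with a principle: "In general, a baseline value refers to the last measurement made prior to the administration of the first dose of the study drug". It also notes that Day 1 assessments may fall on either side of that dose.

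The general rule then builds a pool of eligible records. A record enters the pool if it is dated before the first dose, or if it is one "with an assessment date on the same day of the first dose date and from Day 1 visit or before". A parenthesis restates this last condition as a visit or repeat-visit number strictly below 3. From the pool, "Baseline is the last record after sorting all above records"; the sort keys are assessment date, visit and repeat visit number. Vital signs and ECG are handled separately and take the Day 1 pre-dose value.

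Protocol Section 6 says that the randomisation day "is defined as Day 1 of the study (Visit 3), which is the first day of study drug administration". SAP 3.8.1 agrees on the day: "Study Day 1 (or Day 1) is defined as the first day of administration of randomized study medication", and it uses no Day 0.

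On windows, SAP 3.8.4.2 states: "Visit-windows will only be defined for post-baseline visits and applied to post-baseline data". It keeps dose-monitoring data out of them. Where a quantitative variable has several records in one window, SAP 3.8.6 says "the average of the multiple records will be used".

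**The concern.** The condition in words and the condition in numbers cannot both be programmed. The words include the Day 1 visit. The number excludes it, because that visit is Visit 3. A programmer is likely to code the number, and doing so defeats the principle that opens the section.

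Two consequences follow in domains under the general rule that are collected at Visit 3. First, the change from baseline and percent of baseline would be measured from an older value. Second, the SAP leaves the rejected record without a stated place, although its study day is the start day of every first window. If it were treated as post-baseline, an untreated value would enter an on-treatment summary.

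**Working it through.** The plan states no figure that depends on this rule, so there is none to reproduce. The check is a trace of the rule.

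**1. Which visit is Day 1?** Protocol Sections 5.3, 5.5.4 and 6 put randomisation and first dosing at Visit 3. SAP 3.8.4.1 keeps the protocol's numbering (Visits 4 to 7 for the early visits, 8 to 14 for the quarterly ones). A different numbering in the database is therefore an unlikely explanation.

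**2. Which record is selected?** The study days for Visits 1 and 2 are assumed for illustration; only their order matters.

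| Record | Visit | Study day | Eligible with < 3 | Eligible with ≤ 3 |
|---|---|---|---|---|
| Screening | 1 | −30 | yes | yes |
| Pre-randomisation | 2 | −7 | yes | yes |
| Dosing day, pre-dose | 3 | 1 | no | yes |
| Week 2 | 4 | 14 | no | no |

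With < 3 the last eligible record is Visit 2. With ≤ 3 it is the Visit 3 pre-dose record. Under < 3 the same-day clause admits only a Visit 1 or 2 record that happens to be dated on the dosing day, so it does almost no work. That suggests the words carry the intent.

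**3. Is ≤ 3 enough?** No. The sort keys contain no time and no pre-dose flag. If a Visit 3 assessment followed the dose, ≤ 3 alone could select it as baseline.

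**4. Where could the rejected record go?** By SAP 3.8.1 its study day is (first dose date − first dose date + 1) = 1. The first windows in SAP Tables 3-4 to 3-9 run from Day 1 to Days 22, 270, 22, 135, 60 and 195 respectively. All six contain Day 1. No sentence assigns the record to a window, and none expressly keeps it out.

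**5. What would averaging do, if it happened?** Let B be the older baseline, V the Visit 3 value and W the true Week 2 value. The window value is (V + W)/2, and the reported change is ((V − B) + (W − B))/2. Protocol Section 1.1 gives lymphocyte counts of 20–30% of baseline on fingolimod. Assume a Visit 3 sample exists, is windowed by date, shares the window with one Week 2 sample, and the full effect is present by Week 2. Relative to V, the summary value would then be:

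- true 20%: (1 + 0.20)/2 = 60%
- true 25%: (1 + 0.25)/2 = 62.5%
- true 30%: (1 + 0.30)/2 = 65%

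This illustrates the risk. It does not predict what will happen.

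**6. Which domains?** Protocol Appendix 3, Section 15.4 has white cell, neutrophil and lymphocyte counts taken at every visit, and SAP 6.5.4 reports change and percent of baseline for haematology. For C-SSRS, the Amendment 1 log and the footnotes to Protocol Tables 6-2 and 6-3 point to administration at every visit. Table 6-1, the Core Phase schedule, would settle both.

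**7. What is untouched?** The primary model (SAP 4.2.1) uses treatment, IVRS pubertal status, region and relapse history. The T2 baseline for the key secondary analysis comes from the screening scan (SAP 4.2.2.4).

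**The case against.** The strongest reply is that this is a one-character slip. Two statements in SAP 3.8.2 admit a pre-dose Day 1 record and one parenthesis does not, so a programmer who follows the definition gets the right answer. A ≤ sign might also have lost its underline in conversion to text. The first part is fair, and it is why the point is a contradiction and not a settled exclusion. The second cannot be ruled out, but ≤ survives elsewhere in the SAP (Sections 2 and 6.1.4), and the missing pre-dose check would remain either way.

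It can also be said that Protocol Sections 3.1 and 6 place baseline assessments before randomisation. If laboratory baseline is drawn only then, the older value is the planned one and nothing changes. Section 15.4 is safety guidance, not the visit schedule. This stands until Table 6-1 is checked.

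A reader might infer four stronger things that the documents do not support:

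- That all Day 1 pre-dose data are lost. Vital signs and ECG have their own rule.
- That a rejected record goes into the Week 2 window. Windows are for post-baseline data and exclude dose monitoring; EDSS, MRI and OCT use nominal visits.
- That averaging halves the Week 2 change from baseline. By the formula in step 5, that is true only if V equals B.
- That a pre-dose C-SSRS yes on Day 1 would count as during the study. C-SSRS has no window table, SAP 6.12 has a separate baseline summary, and Protocol 9.5.3 speaks of treatment-emergent events.

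**Conclusion.** The contradiction is real and lies in an operative derivation rule. Coded as the number reads, it replaces the last pre-dose value with an older one in every domain that falls under the general rule and is collected at Visit 3. That consequence needs no assumption about windows. Treatment of the rejected record as post-baseline is a further risk that the SAP leaves open.

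The reach is limited. No confirmatory test, power figure or error rate depends on the rule. What is at stake is safety and descriptive summaries, probably haematology and C-SSRS. The size cannot be fixed from the documents: it depends on how far the older value differs from the Visit 3 value and on how the rejected record is classified. The conclusion assumes that the printed sign is the intended text and that at least one such domain is collected at Visit 3. It should be corrected before the derivations are final, but it does not threaten the trial's main conclusions.

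**What to change.** In SAP 3.8.2, replace the numeric condition with: visit number ≤ 3 and, for records dated on Day 1, assessed before the first dose, judged by time or by a pre-dose label where no time is recorded. Add to SAP 3.8.2 or 3.8.4.2 that a record taken up to the first dose is never assigned to a post-baseline window and never counted as occurring during treatment. Check Table 6-1 and list the domains collected at Visit 3 that have no baseline rule of their own.

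The cost is a line or two in the SAP and the same change in the derivation program. No new data collection is involved, provided a time or pre-dose label exists for the domains concerned.
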